5.3.2 Hematologic Events

For hematologic events, a DLT is defined as follows:

- Grade 4 neutropenia lasting >7 days;
- Grade ≥3 febrile neutropenia;
- Grade 4 anemia;
- Grade 4 thrombocytopenia or ≥ Grade 3 thrombocytopenia lasting >7 days or associated with bleeding; and/or
- Dose delay >7 days secondary to myelosuppression.

Toxicities will be monitored throughout the study, and if the toxicity levels in any Arm are unacceptable (>33% of subjects), then dosing will be suspended until further review and consideration by the SRC.

5.4 Other Adverse Event Considerations

5.4.1 Dose Interruption, Modification, and Management of Events Associated with Study Treatments

In some circumstances, it may be necessary to temporarily interrupt one or more study treatments as a result of adverse events that may have an unclear relationship to study drug.

Any interruptions of >2 weeks or for LFT abnormalities must be discussed with the Study Medical Monitor before resuming treatment. Treatment with all study drugs should be withheld for drug-related Grade 4 hematologic toxicities, nonhematological toxicity \geq Grade 3 (including laboratory abnormalities), and severe or life-threatening adverse events.

Except in cases of emergency, it is recommended that the Investigator consult with the Study Medical Monitor (or other representative of the Sponsor) before temporarily interrupting therapy for reasons other than protocol-mandated medication hold. Additionally, the Investigator must notify the Study Medical Monitor and Study Project Manager via email before restarting study drug that was temporarily interrupted because of an adverse event.

Dosing interruptions may be permitted in the case of medical/surgical events or logistical reasons not related to study therapy (e.g. elective surgery, unrelated medical events, vacation, and/or holidays) upon review and approval from the Study Medical Monitor. Subjects should be placed back on study therapy within 3 weeks of the scheduled interruption, unless otherwise discussed with the sponsor. The reason for interruption should be documented in the subject's study record. Pembrolizumab may be administered up to 3 days before or after the scheduled Day 1 of each cycle due to administrative reasons. CRS-207 must be administered one day after pembrolizumab administration.

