5.4.2 Criteria and Procedures for Dose Modification

CRS-207 has been well tolerated to date. The major safety signals have been infusion related reactions ([Section 5.5.2.1](#)). If a dose reduction of CRS-207 is being considered then the Study Medical Monitor should be contacted for further discussion.

Epacadostat dose may be reduced according to the guidelines and dose levels described in [Table 6](#). Additional information related to dose changes for epacadostat for specific adverse events can be found in [Section 5.4.3.3](#) for immune-related Adverse Events (irAEs) and [Section 5.4.6](#) for an adverse event of SS. Dose modifications for pembrolizumab-related events are provided in [Table 7](#).

If the subject experiences a new TEAE or is recovering from a TEAE, CRS-207 administration may be delayed up to 7 days following pembrolizumab administration; the Sponsor must be notified. If a dose of CRS-207 is delayed beyond 7 days of pembrolizumab, the dose of CRS-207 should be withheld until the next cycle.

Table 6 Dose Modification Guidance for Epacadostat

Toxicity	Hold Treatment For Grade	Timing for Restarting Treatment	Dose Level for Restarting Treatment	Treatment Discontinuation
Diarrhea/Colitis	2-3	Toxicity resolves to Grade 0-1	Related: Reduce by 1 dose level Not Related: Same dose level	Toxicity does not resolve within 12 weeks of last dose or inability to reduce corticosteroid to 10 mg or less of prednisone or equivalent per day within 12 weeks
	4	Permanently discontinue	n/a	Permanently discontinue
AST, ALT, or Increased Bilirubin ¹	2	Toxicity resolves to Grade 0-1	Related: Reduce by 1 dose level Not Related: Same dose level	Toxicity does not resolve within 12 weeks of last dose
	3-4	Permanently discontinue (see exception below) ²	n/a	Permanently discontinue
Type 1 diabetes mellitus (if new onset)	T1DM	Hold epacadostat for new onset Type 1 diabetes mellitus. Resume epacadostat when subjects are clinically and metabolically stable.	Related: Reduce by 1 dose level Not Related: Same dose level	Resume epacadostat when subjects are clinically and metabolically stable
Hyperglycemia	3-4	Hold epacadostat for Grade 3-4 hyperglycemia associated with evidence of beta cell failure. Resume epacadostat when subjects are clinically and metabolically stable.	Related: Reduce by 1 dose level Not Related: Same dose level	Resume epacadostat when subjects are clinically and metabolically stable

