Hypophysitis	2-4	Therapy with epacadostat can be continued while endocrine replacement therapy is instituted.	Related: Reduce by 1 dose level Not Related: Same dose level	Toxicity does not resolve within 12 weeks of last dose or inability to reduce corticosteroid to 10 mg or less of prednisone or equivalent per day within 12 weeks
Hyperthyroidism	3	Toxicity resolves to Grade 0-1	Related: Reduce by 1 dose level Not Related: Same dose level	Toxicity does not resolve within 12 weeks of last dose or inability to reduce corticosteroid to 10 mg or less of prednisone or equivalent per day within 12 weeks
	4	Permanently discontinue	n/a	Permanently discontinue
Hypothyroidism	1-4	Therapy with epacadostat can be continued while thyroid replacement therapy is instituted	n/a	Therapy with epacadostat can be continued while thyroid replacement therapy is instituted
Pneumonitis	2	Toxicity resolves to Grade 0-1	Related: Reduce by 1 dose level	

¹ Subjects with bone metastasis related elevations at baseline, contact sponsor to discuss clinical management and possible dose reductions of epacadostat.

² For subjects with liver metastasis who begin treatment with Grade 2 AST or ALT, if AST or ALT increases by greater than or equal to 50% relative to baseline and lasts for at least 1 week then subjects should be discontinued. For subjects have transient Grade 3 AST/ALT levels persisting for < 7 days and do NOT require steroids, epacadostat may reduce by 1 dose level once AST/ALT returns to baseline.

Toxicity	Hold Treatment For Grade	Timing for Restarting Treatment	Dose Level for Restarting Treatment	Treatment Discontinuation
			Not Related: Same dose level	Toxicity does not resolve within 12 weeks of last dose or inability to reduce corticosteroid to 10 mg or less of prednisone or equivalent per day within 12 weeks
	3-4	Permanently discontinue	n/a	Permanently discontinue
Renal Failure or Nephritis	2	Toxicity resolves to Grade 0-1	Related: Reduce by 1 dose level Not Related: Same dose level	Toxicity does not resolve within 12 weeks of last dose or inability to reduce corticosteroid to 10 mg or less of prednisone or equivalent per day within 12 weeks
	3-4	Permanently discontinue	n/a	Permanently discontinue

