All Other Drug-Related Toxicity	3 or Severe ³	Toxicity resolves to Grade 0-1	Related: Reduce by 1 dose level Not Related: Same dose level	Toxicity does not resolve within 12 weeks of last dose or inability to reduce corticosteroid to 10 mg or less of prednisone or equivalent per day within 12 weeks
	4	Permanently discontinue	n/a	Permanently discontinue

³ Subjects with intolerable or persistent Grade 2 drug-related AE may hold study medication at physician discretion. Permanently discontinue epacadostat for persistent Grade 2 adverse reactions for which treatment with study drug has been held, that do not recover to Grade 0-1 within 12 weeks of the last dose.

Table 7 Pembrolizumab Dose Modification Guidelines for Drug-Related Adverse Events

Toxicity	Hold Treatment For Grade	Timing for Restarting Treatment	Treatment Discontinuation
Diarrhea/Colitis	2-3	Toxicity resolves to Grade 0-1	Toxicity does not resolve within 12 weeks of last dose or inability to reduce corticosteroid to 10 mg or less of prednisone or equivalent per day within 12 weeks
	4	Permanently discontinue	Permanently discontinue
AST, ALT, or Increased Bilirubin	2	Toxicity resolves to Grade 0-1	Toxicity does not resolve within 12 weeks of last dose
	3-4	Permanently discontinue (see exception below) ^a	Permanently discontinue
Type 1 diabetes mellitus (if new onset) or Hyperglycemia	T1DM or 3-4	Hold pembrolizumab for new onset Type 1 diabetes mellitus or Grade 3-4 hyperglycemia associated with evidence of beta cell failure	Resume pembrolizumab when subjects are clinically and metabolically stable
Hypophysitis	2-4	Toxicity resolves to Grade 0-1. Therapy with pembrolizumab can be continued while endocrine replacement therapy is instituted	Toxicity does not resolve within 12 weeks of last dose or inability to reduce corticosteroid to 10 mg or less of prednisone or equivalent per day within 12 weeks
Hyperthyroidism	3	Toxicity resolves to Grade 0-1	Toxicity does not resolve within 12 weeks of last dose or inability to reduce corticosteroid to 10 mg or less of prednisone or equivalent per day within 12 weeks
	4	Permanently discontinue	Permanently discontinue
Hypothyroidism		Therapy with pembrolizumab can be continued while thyroid replacement therapy is instituted	Therapy with pembrolizumab can be continued while thyroid replacement therapy is instituted
Infusion Reaction	2 ^b	Toxicity resolves to Grade 0-1	Permanently discontinue if toxicity develops despite adequate premedication

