5.4.3.3 Discontinuation Rules and Procedures for Immune-Related Adverse Events

Adverse events of a potential immunologic etiology or irAEs may be defined as an adverse event of unknown etiology, associated with drug exposure and consistent with an immune phenomenon. IrAEs may be predicted based on the nature of the compounds, their mechanism of action, and reported experience with immunotherapies that have a similar mechanism of action. Special attention should be paid to adverse events that may be suggestive of potential irAEs. An irAE can occur shortly after the first dose or several months after the last dose of treatment.

If an irAE is suspected, efforts should be made to rule out neoplastic, infectious, metabolic, toxin, or other etiologic causes prior to labeling an adverse event as an irAE. If other causes exist, additional supportive care may be required. Subjects who develop a \geq Grade 2 irAE should be discussed immediately with the Sponsor.

General supportive care recommendations to manage irAEs due to epacadostat are detailed in [Table 8](#). In addition, recommendations for prophylactic and supportive care measures of specific irAEs, infusion reactions, pneumonitis, hepatitis, dermatitis, immune-mediated neuropathies, immune-mediated endocrinopathies, and ocular manifestations are detailed throughout [Section 5.4](#).

irAEs may be attributable to one or more study drugs. If the event is clearly related to one of the agents, follow the instructions specific for that agent, if available. If the event is related to multiple agents, follow the action taken instructions provided, or consult the Study Medical Monitor.

Table 8 General Guidelines for Immune-Related Adverse Events Due to Epacadostat

irAE Toxicity Grade	Withhold/Discontinue Epacadostat*	Action Taken With Respect to Epacadostat	Supportive Care
Grade 1	No action.	Not applicable.	Provide symptomatic treatment.
Grade 2	May withhold epacadostat per Investigator's discretion.	May return to treatment if improves to Grade 1 or resolves within 6 weeks. If adverse event resolves within 4 weeks, subject may restart at the same dose and schedule for epacadostat. For an adverse event that does not resolve within 4 weeks, epacadostat should be reduced 1 dose level. If adverse event does not resolve within 6 weeks, study treatment with epacadostat should be discontinued or discussed with Study Medical Monitor.	Consider systemic corticosteroids in addition to appropriate symptomatic treatment.

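### Section 5.4.1 holds all study drugs for Grade 3 or higher non-hematologic toxicity, but Tables 6 and 7 let epacadostat and pembrolizumab continue through Grade 3-4 hypothyroidism, and nothing says which rule prevails

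*Protocol*

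**What the plan says.** **General rule.** Protocol Section 5.4.1 states: "Treatment with all study drugs should be withheld for drug-related Grade 4 hematologic toxicities, nonhematological toxicity" of Grade 3 or higher, with laboratory abnormalities expressly included. No exceptions are listed, and the sentence does not point to the tables that follow.

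**Drug-specific rules in Section 5.4.2.**
- Hypothyroidism. Table 6, row graded 1-4: "Therapy with epacadostat can be continued while thyroid replacement therapy is instituted". Table 7, grade cell blank: "Therapy with pembrolizumab can be continued while thyroid replacement therapy is instituted".
- Hypophysitis, both rows graded 2-4. Table 6: "Therapy with epacadostat can be continued while endocrine replacement therapy is instituted". Table 7: "Toxicity resolves to Grade 0-1. Therapy with pembrolizumab can be continued while endocrine replacement therapy is instituted".
- Hyperglycemia, Grade 3-4. Table 6: "Hold epacadostat for Grade 3-4 hyperglycemia associated with evidence of beta cell failure". Table 7: "Hold pembrolizumab for new onset Type 1 diabetes mellitus or Grade 3-4 hyperglycemia associated with evidence of beta cell failure".

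**Immune-related events.** Section 5.4.3.3 says: "If the event is clearly related to one of the agents, follow the instructions specific for that agent, if available". Where several agents are implicated, it sends the site to the action-taken instructions or the Study Medical Monitor. The Table 8 footnote refers the question of continuing CRS-207 to the Medical Monitor when epacadostat is held or stopped. Section 5.4.3.2 permanently discontinues all study drugs for Grade 4 immune-related events. The note under Table 7 permanently discontinues pembrolizumab for any life-threatening event.

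**The concern.** A hold rule has to give one answer for one patient. Here a site that reads Section 5.4.1 interrupts the whole regimen for Grade 3 hypothyroidism, while a site that reads Tables 6 and 7 keeps giving epacadostat and pembrolizumab. Both are following the protocol.

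Patient management is the first thing at stake. The second is exposure. SAP Section 6.8 summarizes cycles, CRS-207 infusions, epacadostat mean daily dose and duration of treatment for each drug. If sites resolve the conflict differently, part of the variation in those summaries reflects which passage was read rather than tolerability.

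**Working it through.** There is no figure to reproduce, so the check is textual. It asks what Section 5.4.1 requires, what each table row requires at Grade 3 or higher, and whether any passage ranks the two.

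**Step 1: row by row at Grade 3-4.** Section 5.4.1 gives the same answer for all three conditions: hold all study drugs.

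| Condition | Table 6 (epacadostat) | Table 7 (pembrolizumab) | Relation to 5.4.1 |
|---|---|---|---|
| Hypothyroidism | Continue, Grades 1-4 | Continue, no grade limit | Opposite in both tables |
| Hypophysitis | Grades 2-4 in the hold column; text says continue; restart cell gives a dose level | Grades 2-4 in the hold column; one cell holds both a resolve-to-Grade-0-1 condition and permission to continue | Unclear in both tables |
| Hyperglycemia | Hold stated only with beta cell failure | Hold stated only with new-onset type 1 diabetes or beta cell failure | Narrower, but not opposite |

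The remaining rows with Grade 3 or higher entries hold or discontinue the drug concerned, which agrees with Section 5.4.1 for that drug. The count is one condition with a direct contradiction in both tables, one with unclear wording, and one where the tables say less than Section 5.4.1.

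**Step 2: does the drug-related qualifier remove the conflict?** In Section 5.4.1 it precedes the first list item, and the text does not say whether it governs the rest.
- If it covers only the hematologic item, the hold applies to Grade 3-4 hypothyroidism of any cause.
- If it covers the whole list, the hold applies to drug-related Grade 3-4 hypothyroidism. Table 7 is titled for drug-related events, and the Table 6 hypothyroidism row makes no distinction by relatedness.

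The contradiction stands on either reading.

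**Step 3: is there a precedence rule?** Section 5.4.3.3 is the nearest. It applies to immune-related events, directs the site to the related agent's instructions when one agent is clearly responsible, and does not mention Section 5.4.1. It also does not say what happens to the other agents, all of which Section 5.4.1 holds. For epacadostat it leaves a choice: the Table 6 hypothyroidism row continues the drug, while the Grade 3 row of Table 8 withholds or discontinues it.

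**Step 4: CRS-207.** It has no dose-modification table by toxicity. Section 5.4.1 holds it with the others. The Table 8 footnote sends the decision to the Medical Monitor, but only where epacadostat has been held or stopped. A site that continues epacadostat under Table 6 does not reach that footnote.

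**Step 5: Grade 4.** Besides holding and continuing there is a third instruction: permanent discontinuation of all study drugs (Section 5.4.3.2, immune-related events) or of pembrolizumab (Table 7 note, life-threatening events). Both conflict with the rows permitting continuation.

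**Step 6: DLT counts.** Under Section 5.3.1 a Grade 3 or higher non-hematologic TEAE in Cycle 1 not attributable to disease is already a DLT, unless exempted, whether or not drug is held. A hold can change DLT status only if three things coincide: the event is on the exemption list, the interruption exceeds 7 days, and the relationship to study drug is unclear. For hypothyroidism, the one clean contradiction, holding or continuing would not ordinarily change DLT status.

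**The case against.** The strongest reply is that specific guidance displaces general guidance, that Section 5.4.3.3 already routes these events, and that the sponsor would hear of them. Much of this is fair. All three conditions appear in the immune-related guidance of Section 5.4.3.1. Section 5.4.3.3 requires immediate discussion with the sponsor from Grade 2. Section 9.1.2 makes Grade 3 or higher hypothyroidism an event of special interest, reportable within 24 hours. Section 5.4.1 requires notice to the Medical Monitor before a drug interrupted for an adverse event is restarted. Divergence between sites would therefore often be noticed.

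The reply does not settle the matter. No passage says that the tables override Section 5.4.1. Discussion with the sponsor does not tell a site what to do in the meantime. Section 5.4.1 recommends consultation before a temporary interruption only when the hold is not mandated by the protocol, and whether this one is mandated is the open question.

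The other side is right to resist several stronger readings that a reader might infer:
- **That three conditions carry opposite instructions in each table.** Neither table says to keep dosing in hyperglycemia without beta cell failure. The row is silent there, and the catch-all row for other drug-related toxicity (hold at Grade 3, discontinue at Grade 4) may apply. The Table 7 hypophysitis cell can be read as hold and then resume, and the Table 6 restart dose presupposes a hold.
- **That every Grade 3 or higher non-hematologic event is caught.** This depends on the reach of the drug-related qualifier.
- **That any event attributed to one agent could lead to one, two or three drugs being held.** The Section 5.4.3.3 rule covers immune-related events only, and only one arm receives three drugs.
- **That DLT counts are generally at risk.** Step 6 of the working shows that the route is narrow.

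**Conclusion.** The inconsistency is real and can be shown from the protocol alone. It is a direct contradiction for Grade 3-4 hypothyroidism, covering both epacadostat and pembrolizumab. In the three-drug arm the choice is between holding all three drugs and holding neither of the two that the tables address, with CRS-207 left open. Hypophysitis needs clearer wording. Hyperglycemia needs a statement of what applies without beta cell failure. Grade 4 adds a conflict with the permanent-discontinuation instructions.

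The conclusion assumes that the blank grade cell in the Table 7 hypothyroidism row means no grade limit. If that cell is incomplete, the Table 6 row, graded 1-4, still carries the contradiction for epacadostat. How often these events occurred cannot be judged from the documents.

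The practical reach is now small. SAP Section 3.5 records that development ceased on 12 December 2017 and that, as of 12 January 2018, all but 2 subjects had completed their end-of-treatment visit; those 2 had the option to continue. This is a protocol inconsistency that should be corrected, not a flaw in the efficacy design.

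**What to change.** Reconcile Section 5.4.1 with Tables 6 and 7, Sections 5.4.3.2 and 5.4.3.3, and Table 8 with its footnote. The revised text should state:

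1. which passage governs when they differ;
2. whether the drug-related qualifier applies to the whole Section 5.4.1 list;
3. for hypothyroidism, hypophysitis and hyperglycemia at Grade 3 and at Grade 4, which study drugs the Section 5.4.1 hold covers, CRS-207 included;
4. whether the grades in the hold column of the hypophysitis rows, and of the Table 6 hypothyroidism row, are meant to trigger a hold.

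The clinical content of each answer is for the sponsor and investigators; this review takes no view on it. The cost is a protocol wording change or a clarification letter to sites, with no added visits, procedures or subjects.

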5.4.2 Criteria and Procedures for Dose Modification

CRS-207 has been well tolerated to date. The major safety signals have been infusion related reactions ([Section 5.5.2.1](#)). If a dose reduction of CRS-207 is being considered then the Study Medical Monitor should be contacted for further discussion.

Epacadostat dose may be reduced according to the guidelines and dose levels described in [Table 6](#). Additional information related to dose changes for epacadostat for specific adverse events can be found in [Section 5.4.3.3](#) for immune-related Adverse Events (irAEs) and [Section 5.4.6](#) for an adverse event of SS. Dose modifications for pembrolizumab-related events are provided in [Table 7](#).

If the subject experiences a new TEAE or is recovering from a TEAE, CRS-207 administration may be delayed up to 7 days following pembrolizumab administration; the Sponsor must be notified. If a dose of CRS-207 is delayed beyond 7 days of pembrolizumab, the dose of CRS-207 should be withheld until the next cycle.

Table 6 Dose Modification Guidance for Epacadostat

Toxicity	Hold Treatment For Grade	Timing for Restarting Treatment	Dose Level for Restarting Treatment	Treatment Discontinuation
Diarrhea/Colitis	2-3	Toxicity resolves to Grade 0-1	Related: Reduce by 1 dose level Not Related: Same dose level	Toxicity does not resolve within 12 weeks of last dose or inability to reduce corticosteroid to 10 mg or less of prednisone or equivalent per day within 12 weeks
	4	Permanently discontinue	n/a	Permanently discontinue
AST, ALT, or Increased Bilirubin ¹	2	Toxicity resolves to Grade 0-1	Related: Reduce by 1 dose level Not Related: Same dose level	Toxicity does not resolve within 12 weeks of last dose
	3-4	Permanently discontinue (see exception below) ²	n/a	Permanently discontinue
Type 1 diabetes mellitus (if new onset)	T1DM	Hold epacadostat for new onset Type 1 diabetes mellitus. Resume epacadostat when subjects are clinically and metabolically stable.	Related: Reduce by 1 dose level Not Related: Same dose level	Resume epacadostat when subjects are clinically and metabolically stable
Hyperglycemia	3-4	Hold epacadostat for Grade 3-4 hyperglycemia associated with evidence of beta cell failure. Resume epacadostat when subjects are clinically and metabolically stable.	Related: Reduce by 1 dose level Not Related: Same dose level	Resume epacadostat when subjects are clinically and metabolically stable
Hypophysitis	2-4	Therapy with epacadostat can be continued while endocrine replacement therapy is instituted.	Related: Reduce by 1 dose level Not Related: Same dose level	Toxicity does not resolve within 12 weeks of last dose or inability to reduce corticosteroid to 10 mg or less of prednisone or equivalent per day within 12 weeks
Hyperthyroidism	3	Toxicity resolves to Grade 0-1	Related: Reduce by 1 dose level Not Related: Same dose level	Toxicity does not resolve within 12 weeks of last dose or inability to reduce corticosteroid to 10 mg or less of prednisone or equivalent per day within 12 weeks
	4	Permanently discontinue	n/a	Permanently discontinue
Hypothyroidism	1-4	Therapy with epacadostat can be continued while thyroid replacement therapy is instituted	n/a	Therapy with epacadostat can be continued while thyroid replacement therapy is instituted
Pneumonitis	2	Toxicity resolves to Grade 0-1	Related: Reduce by 1 dose level	

¹ Subjects with bone metastasis related elevations at baseline, contact sponsor to discuss clinical management and possible dose reductions of epacadostat.

² For subjects with liver metastasis who begin treatment with Grade 2 AST or ALT, if AST or ALT increases by greater than or equal to 50% relative to baseline and lasts for at least 1 week then subjects should be discontinued. For subjects have transient Grade 3 AST/ALT levels persisting for < 7 days and do NOT require steroids, epacadostat may reduce by 1 dose level once AST/ALT returns to baseline.

Toxicity	Hold Treatment For Grade	Timing for Restarting Treatment	Dose Level for Restarting Treatment	Treatment Discontinuation
			Not Related: Same dose level	Toxicity does not resolve within 12 weeks of last dose or inability to reduce corticosteroid to 10 mg or less of prednisone or equivalent per day within 12 weeks
	3-4	Permanently discontinue	n/a	Permanently discontinue
Renal Failure or Nephritis	2	Toxicity resolves to Grade 0-1	Related: Reduce by 1 dose level Not Related: Same dose level	Toxicity does not resolve within 12 weeks of last dose or inability to reduce corticosteroid to 10 mg or less of prednisone or equivalent per day within 12 weeks
	3-4	Permanently discontinue	n/a	Permanently discontinue
All Other Drug-Related Toxicity	3 or Severe ³	Toxicity resolves to Grade 0-1	Related: Reduce by 1 dose level Not Related: Same dose level	Toxicity does not resolve within 12 weeks of last dose or inability to reduce corticosteroid to 10 mg or less of prednisone or equivalent per day within 12 weeks
	4	Permanently discontinue	n/a	Permanently discontinue

³ Subjects with intolerable or persistent Grade 2 drug-related AE may hold study medication at physician discretion. Permanently discontinue epacadostat for persistent Grade 2 adverse reactions for which treatment with study drug has been held, that do not recover to Grade 0-1 within 12 weeks of the last dose.

Table 7 Pembrolizumab Dose Modification Guidelines for Drug-Related Adverse Events

Toxicity	Hold Treatment For Grade	Timing for Restarting Treatment	Treatment Discontinuation
Diarrhea/Colitis	2-3	Toxicity resolves to Grade 0-1	Toxicity does not resolve within 12 weeks of last dose or inability to reduce corticosteroid to 10 mg or less of prednisone or equivalent per day within 12 weeks
	4	Permanently discontinue	Permanently discontinue
AST, ALT, or Increased Bilirubin	2	Toxicity resolves to Grade 0-1	Toxicity does not resolve within 12 weeks of last dose
	3-4	Permanently discontinue (see exception below) ^a	Permanently discontinue
Type 1 diabetes mellitus (if new onset) or Hyperglycemia	T1DM or 3-4	Hold pembrolizumab for new onset Type 1 diabetes mellitus or Grade 3-4 hyperglycemia associated with evidence of beta cell failure	Resume pembrolizumab when subjects are clinically and metabolically stable
Hypophysitis	2-4	Toxicity resolves to Grade 0-1. Therapy with pembrolizumab can be continued while endocrine replacement therapy is instituted	Toxicity does not resolve within 12 weeks of last dose or inability to reduce corticosteroid to 10 mg or less of prednisone or equivalent per day within 12 weeks
Hyperthyroidism	3	Toxicity resolves to Grade 0-1	Toxicity does not resolve within 12 weeks of last dose or inability to reduce corticosteroid to 10 mg or less of prednisone or equivalent per day within 12 weeks
	4	Permanently discontinue	Permanently discontinue
Hypothyroidism		Therapy with pembrolizumab can be continued while thyroid replacement therapy is instituted	Therapy with pembrolizumab can be continued while thyroid replacement therapy is instituted
Infusion Reaction	2 ^b	Toxicity resolves to Grade 0-1	Permanently discontinue if toxicity develops despite adequate premedication
	3-4	Permanently discontinue	Permanently discontinue
Pneumonitis	2	Toxicity resolves to Grade 0-1	Toxicity does not resolve within 12 weeks of last dose or inability to reduce corticosteroid to 10 mg or less of prednisone or equivalent per day within 12 weeks
	3-4	Permanently discontinue	Permanently discontinue
Renal Failure or Nephritis	2	Toxicity resolves to Grade 0-1	Toxicity does not resolve within 12 weeks of last dose or inability to reduce corticosteroid to 10 mg or less of prednisone or equivalent per day within 12 weeks
	3-4	Permanently discontinue	Permanently discontinue
All Other Drug-Related Toxicity ^c	3 or Severe	Toxicity resolves to Grade 0-1	Toxicity does not resolve within 12 weeks of last dose or inability to reduce corticosteroid to 10 mg or less of prednisone or equivalent per day within 12 weeks
	4	Permanently discontinue	Permanently discontinue

Note: Permanently discontinue for any severe or Grade 3 (Grade 2 for pneumonitis) drug-related AE that recurs or any life-threatening event.
 
^a For subjects with liver metastasis who begin treatment with Grade 2 AST or ALT, if AST or ALT increases by greater than or equal to 50% relative to baseline and lasts for at least 1 week then subjects should be discontinued. Grade 3 AST/ALT levels persisting for < 7 days, pembrolizumab may resume once AST/ALT has returns to baseline.
 
^b If symptoms resolve within one hour of stopping drug infusion, the infusion may be restarted at 50% of the original infusion rate (e.g. from 100 mL/hr to 50 mL/hr). Otherwise dosing will be held until symptoms resolve and the subject should be pre-medicated for the next scheduled dose; Refer to Table 9 for further management details.
 
^c Subjects with intolerable or persistent Grade 2 drug-related AE may hold study medication at physician discretion. Permanently discontinue study drug for persistent Grade 2 adverse reactions for which treatment with study drug has been held, that do not recover to Grade 0-1 within 12 weeks of the last dose.
			

